Telehealth Cognitive Behavioral Therapy for Depression
in Parkinson's Disease (PD)

ClinicalTrials.gov ID: NCT02475954

Document Date: 6/18/15

Title of Project: Telehealth Cognitive Behavioral Therapy for Depression in Parkinson's Disease (PD)

Principal Investigator: [name].

Funding Source(s): VA HSR&D

1. Purpose/Specific Aims

There is a critical need for treatments that address depression and barriers to mental health care among the nearly 100,000 Veterans with Parkinson's disease (PD) served by the VA. Depression in PD (dPD) is a major complicating factor in the movement disorder, affecting several key functional outcomes such as motor disability, cognitive status, quality of life, and Care-partner relationships.¹⁻⁴ The challenge to meeting the treatment needs of Veterans with dPD centers on the lack of clinicians who are knowledgeable about the interactions of PD and depression, the considerable transportation barriers faced by this population, combined with the geographical dispersion of specialized services within the VA, and the paucity of effectiveness research that informs treatments for dPD.⁵

To address this problem, we propose to conduct a randomized controlled trial (RCT) to test the effectiveness of a psychotherapeutic intervention aimed at treating depression in Parkinson's disease (dPD) in Veterans. The proposed study treatment consists of a 10-session cognitive-behavioral treatment (CBT) package that has been tailored to address the unique needs of depressed Veterans with PD. Also, the treatment seeks to overcome treatment access barriers by using telehealth delivery platform (i.e., video-to-home telehealth technology). In addition, the proposed treatment package provides support and skills-training to the Veteran's Care-partner (3 sessions).

1.1 Objectives

AIM 1: To evaluate the effectiveness of TH-CBT (telehealth-cognitive behavioral therapy) for improving Veteran outcomes in dPD (depression in Parkinson's Disease).

AIM 2: To examine the impact of TH-CBT for dPD on a variety of Care-partner outcomes.

AIM 3: To assess Veteran and Care-partner perspectives on TH-CBT using qualitative, semi-structured interviews.

1.2 Hypotheses

Primary Hypotheses: Depressive symptoms will decrease more for Veterans receiving TH-CBT (the "intervention group"), than for Veterans receiving standard care only (the "control group").

Secondary Hypotheses: There will be more treatment responders in the TH-CBT group (the "intervention group") than in the standard care group (the "control group)." Psychiatric and functional correlates of dPD for Veterans receiving TH-CBT will show greater improvement (anxiety, quality of life) or stabilization (motor disability) over time than those for Veterans in the standard care group.

Care-partner Hypotheses: Care-partners in the TH-CBT condition (the "intervention group") will feel more empowered, report less distress and be less critical (towards the Veteran) relative to Care-partners in the standard care group (the "control group").

2. Background and Significance

Depression, the most common non-motor complaint in PD, ¹ affects up to 50% of PD patients.⁶ Depression in PD (dPD) is associated with rapid physical and cognitive decline,² poorer quality of life,⁷ increased healthcare costs,⁸ earlier initiation of dopaminergic replacement,⁹ and notable Care-partner distress.³ Depression is therefore a key intervention target for improving a range of PD complications.

Yet, unfortunately, depression treatment is the one quality standard inadequately addressed in VA PD care, including in its PD specialty centers.^{10,11} Sub-optimally treated dPD aggravates physical and cognitive PD morbidity, thereby undermining all of the VA's other evidence-based efforts to improve non-mental health disturbances for PD Veterans.^{2,10,12} Thus, there is a critical need for treatments that address depression and barriers to care among the approximately 100,000 Veterans with PD.¹³

The challenge to addressing depression in PD centers on the lack of mental health clinicians who are knowledgeable about the movement disorder (a prerequisite to effective care), the transportation barriers faced by Veterans, the geographical dispersion of VA services, and the paucity of effectiveness research that informs depression treatments for PD Veterans.⁵

The proposed study seeks to overcome these obstacles by using a telehealth delivery platform (i.e., video-to-home; "V2H" or "CVT-H") to test the effectiveness of a 10-session cognitive-behavioral treatment (CBT) package, tailored to address the unique needs of Veterans with dPD. Preliminary studies provide strong support for the current trial. **V2H allows Veterans to use their computer's webcam to interact with their providers using videoconferencing, via the VA's secure telehealth connection.**

The current trial builds on several earlier trials that have shown support for this intervention to treat depression in PD.

First, this CBT package was initially tested in a face-to-face RCT with 80 people with dPD (and Care-partners), who were randomized to receive CBT plus standard care or standard care only for 10 weeks. The Hamilton Depression Rating Scale ¹⁴ (HAM-D 17) was the primary outcome. Treatment response was defined a priori as a rating of a 1 or 2 on the Clinical Global Impression-Improvement Scale ¹⁵ (CGI-I; a 7 point scale with scores ranging from 1 [very much improved] to 7 [very much worse]) or ≥50% reduction in the baseline HAM-D 17 score. Patients were evaluated at baseline, midpoint (week 5), endpoint (week 10), and one-month follow-up (week 14). CBT was associated with greater improvements in depression, [HAM-D 17; F(3,215)=30.74 P<.0001; Cohen's d=1.59] & Beck Depression Inventory (BDI) F(3,210)=9.77 P=.001; Cohen's d=1.10], anxiety [F(3,214)=11.65 P=.001; Cohen's d=.98], quality of life [F(3,209)=5.07 P=.02, Cohen's d=.81], coping [F(3,204)=4.25, P=.05; Cohen's d=.80] , and motor disability [F(1,68)=5.9 P=.02; Cohen's d=.13] vs. control. At week 10, 56% patients receiving CBT and 8% receiving standard care were treatment responders, as defined above (Fisher's exact P<.0001). At week 14, 51% of CBT patients and 0% of patients in the standard group met criteria for response (Fisher's exact P <.0001).

Second, this treatment was repeated in an uncontrolled trial, where the intervention was delivered via telephone. Within group CBT effect sizes for telephone delivery showed a similar treatment effect, compared to effect sizes obtained via face-to-face delivery. This telephone-based CBT protocol was provided to 21 patients and Care-partners, resulting in significant improvements in depression [HAM-D

17: $F(3,56)=18.50, P<.0001$; Cohen's $d=1.21$ and BDI: $F(3,53)=23.68, P<.0001$]. This trial demonstrated that the same treatment can be delivered remotely with a similar level of treatment impact.

Combined, these initial studies provide support for the CBT package and for its remote delivery (i.e., telehealth). The current trial therefore proposed to test the delivery of this treatment via video-to-home telehealth. This modality of care has been rolled out by the VHA and therefore provides an existing infrastructure to make this intervention available to Veterans with dPD, who face access barriers to treatment. For example, at VA New Jersey, 583 mental health encounters have been conducted via video-to-home telehealth in FY14.

3. Research Design and Methods

Participants will include 90 Veterans (ages 35-85) with dPD and their Care-partners (N=180 total: 90 Veterans with PD and 90 Care-partners). Since Care-partners will be designated by their Veteran with PD, they will not likely be Veterans themselves. The justification for including nonveterans is due to the fact that Care-partners serve as an integral part of the treatment team for Veterans with dPD. Thus, we are evaluating the clinical effectiveness of an intervention that involves Care-partners in order to optimize Veteran depression treatment response and Care-partner well-being.

The clinical effectiveness of a 10-session telehealth-based cognitive-behavioral treatment package (TH-CBT) for dPD will be evaluated. Study conditions are as follows:

- [Intervention] Half of the Veterans will receive telehealth-based CBT, in addition to their standard care (i.e., treatment-as-usual under the care of their personal physicians).
- [Control] The other half will receive their standard care only during the study period. Participants will be randomly assigned to treatment group via computer generated random assignment. Randomization will be stratified by antidepressant use at baseline (yes/no).

Veterans will be evaluated remotely, via telephone, prior to treatment (week 0), mid-way through treatment (week 5), immediately after treatment (week 10), one month following treatment, and six months following treatment by raters who are blind to treatment condition. A purposive subsample of 40 treatment recipients (20 Veterans/20 Care-partners; will receive a semi-structured interview (i.e., exit interview) at Week 10, in order to generate qualitative data on their experience with the study. Specifically, these interviews will focus on 10 Veterans (and their Care-partner) who respond at endpoint (i.e., CGI-I of 1 or 2) and 10 (and their Care-partner) who do not respond (i.e. CGI-I of 4 or 5) to TH-CBT.

Participants will receive the study treatment at no cost. Veterans and Care-partners will each receive \$45 per outcome assessment completed. Data collection ends for all participants at the 6-month follow-up. However, since we expect that our Veteran population will not have access to a needed tailored psychotherapy for dPD (TH-CBT), we will offer this clinical care to control group participants, after the data collection period. However, no additional data will be collected. The total duration of the protocol is 9 months for all participants.

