3.3 Sample Size Justification & Subject Selection

The study will enroll a total of 180 subjects (90 Veterans + 90 of their Care-partners), from VA New Jersey, who have Parkinson's Disease and depression. 1,199 Veterans with dPD were served in VA New Jersey during the last four fiscal years. Several methods of recruitment (see Recruitment and Consent below) will be used to enroll this pool of Veterans.

Our Power Analyses assume 180 participants (90 enrolled dyads) with 144 participants (72 dyads, 36 dyads each arm), completing the study. Observed standard deviations in the power calculations that follow are taken from control group baseline data in [name] et al.¹⁶ For the primary test of treatment differences in HAM-D scores, controlling for baseline HAM-D scores and demographic covariates, the current study is powered to detect a 2.5 point HAM-D treatment difference between groups. For comparison, we observed a group difference of 7.30 in [name] et al.¹⁶ For the secondary test of responder/nonresponder, we considered clinical response rates of 0.05 and 0.10 for the control group and .35, .40, and .45 for the treatment group. Power was greater than .95 in all cases. For comparison, we observed rates of 0.08 and 0.56 in the control and treatment groups, respectively, in [name] et al. (2011).

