Unless otherwise indicated, all of the analyses below will use mixed models analysis to examine treatment effects on the specified dependent variable. There will be one between-group variable (TH-CBT versus control), one repeated measure variable (time), and group-by-time interactions (effect of interest). We will consider several correlational structures between repeated measures (e.g., compound symmetry) and determine the best structure using the Akaike's Information Criterion (AIC). Random effects will be specified for each subject. For each dependent variable, we will analyze the effect of interest (i.e., group X time) separately at each post-randomization assessment point. The models will include demographic covariates (age, sex) as indicated. Standard residual diagnostics will be applied. In the event of unaccounted-for outliers, analyses will be run with and without the outliers. Should the residuals deviate unacceptably from normality assumptions, we will use robust estimation as described and cataloged by Wilcox.³⁵

AIM 1: To evaluate the effectiveness of TH-CBT for improving Veteran outcomes in dPD. Primary Hypothesis: Depressive symptoms will decrease more for Veterans receiving TH-CBT, than for Veterans in the control group. The HAM-D is the primary depression outcome measure. Secondary Hypotheses. There will be more treatment responders in the TH-CBT group. Analyses examining depression treatment response will utilize the CGI-I (response equals CGI-I score of 1- 2).³⁶ Fisher's exact test will be used to test the hypothesis related to treatment response. A sensitivity analysis will be performed using logistic regression to examine the possible importance of covariates. Secondary Hypotheses: Secondary

outcome measures for Veterans receiving TH-CBT will show greater improvement (BDI, HAM-A, SF-36) over time than for those of Veterans in the control group. As these measures can be expected to be correlated, the significance threshold adjusting for multiple-testing will be determined by permutation-based analysis.

AIM 2: To examine the impact of TH-CBT for dPD on a variety of Care-partner outcomes. Hypotheses: TH-CBT Care-partners will feel more empowered (FES), report less distress (CDS) and be less critical (to the Veteran; PCS) relative to controls. The analysis approach will be the same as in Specific Aim 1

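### Do the motor-disability hypothesis and the responder test without a named visit leave secondary analyses undefined?

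*Combined protocol and SAP*

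**What the plan says.** **Motor disability.** The secondary hypotheses in Section 1.2 cover treatment response and three correlates of depression. Anxiety and quality of life are expected to improve more under TH-CBT, and the third is worded as "stabilization (motor disability) over time than those for Veterans in the standard care group". Section 5 restates the hypothesis for the secondary measures, which "will show greater improvement (BDI, HAM-A, SF-36) over time". Motor disability and the idea of stabilization do not reappear there.

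**Response.** Sections 4.2 and 5 define a responder by CGI-I of 1 or 2 alone. Section 5 says that Fisher's "exact test will be used to test the hypothesis related to treatment response" and gives no visit. Its general rule is "Unless otherwise indicated, all of the analyses below will use mixed models analysis", with the group-by-time effect examined "separately at each post-randomization assessment point". For the correlated secondary measures, "the significance threshold adjusting for multiple-testing will be determined by permutation-based analysis". Section 3.3 gives the responder test its own power statement, for which "we considered clinical response rates of 0.05 and 0.10 for the control group", with 0.35, 0.40 and 0.45 in the treatment group and 36 completers per arm.

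**Schedule.** Table 1, as available, has no row for CGI-I or for a motor measure. The Assessments paragraph of Section 3.4.3 names HAM-D and HAM-A as the clinician-rated follow-up instruments.

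**The concern.** A stated hypothesis with no listed outcome has to be dropped or improvised when the report is written. The prior trial in Section 2 reported motor disability as a separate result, so the clause in Section 1.2 does not look accidental.

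The response question seems more serious. There are four post-baseline visits (weeks 5 and 10, then 1 and 6 months after treatment). Fisher's test has no time term, so the visit-by-visit rule written for the mixed models does not plainly cover it. If it did, there would be four tests with no deciding one, and the permutation threshold is stated for BDI, HAM-A and SF-36 rather than for response. The prior trial tested response twice: after the week-10 comparison it also reported "At week 14, 51% of CBT patients and 0% of patients in the standard group met criteria for response". An analyst could in principle choose the visit after seeing the results. Nor does any schedule entry explicitly provide for CGI-I ratings in controls.

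**Working it through.** **1. Motor disability: the sections side by side**

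| Place | Content |
|---|---|
| Section 1.2 | anxiety, quality of life, motor disability |
| Section 4.2 | CGI-I response, BDI-II, HAM-A, SF-36; the sentence then ends on a comma |
| Table 1 | available text breaks between the SF-36 and MoCA rows |
| Section 5 | BDI, HAM-A, SF-36 (complete sentence) |
| Protocol Amendments | no motor measure |

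The mismatch between Sections 1.2 and 5 is real. Whether a measure was scheduled cannot be decided from the text, because both places that would show it are broken. There are two cases:
- If a measure is scheduled, the default mixed model in Section 5 already supplies its analysis.
- If none is scheduled, there are no data and nothing to test.

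In neither case does editing Section 1.2 alter a result.

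**2. Which visit, and which arms**

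- Section 3 and the Qualitative Data paragraph of Section 3.4.3 classify responders by CGI-I at endpoint. The Assessments paragraph of 3.4.3 sets endpoint at week 10.
- Section 3.3 compares its planning rates for this test with 0.08 and 0.56. Section 2 reports 8% and 56% at week 10, and 0% and 51% at week 14. The benchmark is therefore the week-10 result.
- Section 4.2 lists responder status among measures given to the Veteran, with no limit to one arm. The note to Table 1 restricts only Aim 3 measures to TH-CBT, and response belongs to Aim 1. Section 3.4.3 has blinded evaluators do all post-baseline assessments. A between-group Fisher's test also requires ratings in both arms.

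**3. Size of the possible harm**

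Inputs: 36 per arm, control rates 0.05 and 0.10 and treatment rates 0.35, 0.40 and 0.45 (Section 3.3); control rate 0.08 (Section 2). Assumptions: two-sided 5% level, which the documents do not state, and exchangeable latent-normal correlation of 0.3 to 0.9 between visits.

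The rejection probability of Fisher's test is the sum, over all pairs (x, y) with Fisher p ≤ α, of Bin(x; 36, p1) × Bin(y; 36, p2).

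The plan's own figure first. Exact power at one visit:

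| Control v treatment | α = 5% | α = 5%/4 = 1.25% | Loss (points) |
|---|---|---|---|
| 0.05 v 0.35 | 0.884 | 0.730 | 15 |
| 0.05 v 0.40 | 0.952 | 0.859 | 9 |
| 0.05 v 0.45 | 0.983 | 0.937 | 5 |
| 0.10 v 0.35 | 0.653 | 0.427 | 23 |
| 0.10 v 0.40 | 0.800 | 0.602 | 20 |
| 0.10 v 0.45 | 0.901 | 0.758 | 14 |

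Four of the six values in the 5% column fall below the power of more than 0.95 claimed in Section 3.3. That is a separate matter, and nothing here rests on it. The 1.25% column applies only if four visits share the 5% equally, which the plan nowhere proposes. At the benchmark of 0.08 v 0.56 that split would cost 99.5% − 97.6% = about 2 points.

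False-positive rate with no true effect:

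| Common response rate | One fixed visit (exact) | Best of four visits (simulated) |
|---|---|---|
| 5% | 0.3% | 1.0% to 1.2% |
| 8% | 0.9% | 2.9% to 3.7% |
| 10% | 1.4% | 4.0% to 5.3% |

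The ratio of best-of-four to one visit is 2.9 to 4.2. It starts from a very low base because Fisher's test is conservative at low rates, and the absolute rate stays near or below 5%.

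**The case for a change.** The strongest case on the other side is that the gaps do not all come from damaged text. The Fisher's exact sentence and the secondary list in Section 5 are complete, and so is the list in Section 3.4.3 that omits CGI-I. Week 10 is inferred from the choice of interviewees and from a power benchmark; it is not stated for the between-group test. The benchmark rates also come from the prior trial's wider definition, which counted a HAM-D fall of at least 50% as response too. They therefore speak to timing and do not serve as like-for-like rates. If both arms truly responded at 20% to 30%, choosing the best of four visits would give an error of about 7% to 11%.

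The textual part of this stands: the motor clause is unmatched and the visit is unwritten. The consequence does not follow. The 7% to 11% needs null response rates above those used in Section 3.3, and an analyst who passes over the one visit at which the protocol itself classifies responders. The list in 3.4.3 can be read as illustrative, and the missing Table 1 row may be lost text.

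**Conclusion.** No change to the plan follows. The motor clause is a slip of consistency between Sections 1.2 and 5. Aligning the wording would be tidy, but it would add no data and change no result, and deleting a hypothesis because of a possibly incomplete table would go beyond the evidence. The unnamed visit is a gap that an analyst fills sensibly with week 10, in both arms, with other visits as supporting description.

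The possible harm is small on the plan's own rates: best-of-four error of 1.0% to 5.3%, and no loss of power unless a four-way split is adopted that the plan does not contain. These figures rest on 36 completers per arm, a two-sided 5% level, control rates of 5% to 10% and between-visit correlations of 0.3 to 0.9. The primary HAM-D comparison is not affected.

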3.1. Duration of Study

This is a four-year study that will actively recruit subjects for a period of approximately 3.5 years. Subjects enrolled in the study will participate in the protocol for approximately 9 months.

3.2 Study Sites

Subjects will be Veterans of VA New Jersey Healthcare System. VA New Jersey will be the only site engaged in Human subjects research.

3.3 Sample Size Justification & Subject Selection

The study will enroll a total of 180 subjects (90 Veterans + 90 of their Care-partners), from VA New Jersey, who have Parkinson's Disease and depression. 1,199 Veterans with dPD were served in VA New Jersey during the last four fiscal years. Several methods of recruitment (see Recruitment and Consent below) will be used to enroll this pool of Veterans.

Our Power Analyses assume 180 participants (90 enrolled dyads) with 144 participants (72 dyads, 36 dyads each arm), completing the study. Observed standard deviations in the power calculations that follow are taken from control group baseline data in [name] et al.¹⁶ For the primary test of treatment differences in HAM-D scores, controlling for baseline HAM-D scores and demographic covariates, the current study is powered to detect a 2.5 point HAM-D treatment difference between groups. For comparison, we observed a group difference of 7.30 in [name] et al.¹⁶ For the secondary test of responder/nonresponder, we considered clinical response rates of 0.05 and 0.10 for the control group and .35, .40, and .45 for the treatment group. Power was greater than .95 in all cases. For comparison, we observed rates of 0.08 and 0.56 in the control and treatment groups, respectively, in [name] et al. (2011).

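### Responder power is stated as above .95 in every scenario, but with 36 completers per arm and Fisher's exact test it runs from .65 to .98 and passes .95 in only two of six

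*Combined protocol and SAP*

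**What the plan says.** Section 3.3 (Sample Size Justification & Subject Selection) starts from 90 enrolled dyads and plans on "144 participants (72 dyads, 36 dyads each arm), completing the study". For the responder comparison it says "we considered clinical response rates of 0.05 and 0.10 for the control group and .35, .40, and .45 for the treatment group", which makes six pairs, and concludes: "Power was greater than .95 in all cases". It adds that the earlier face-to-face trial observed response rates of .08 and .56.

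Section 5 (Data Handling and Statistical Analysis, Aim 1) defines response as a CGI-I score of 1 or 2 and says that Fisher's "exact test will be used to test the hypothesis related to treatment response". Logistic regression with covariates is a sensitivity analysis only. Neither section gives a significance level, a sidedness or a power formula for this test. Section 5 mentions a permutation-based multiplicity threshold, placed directly after the BDI, HAM-A and SF-36.

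**The concern.** The rates, the number per arm and the test are all given, so the power statement can be checked directly. A difference of .10 against .35 with 36 per arm is not one that a two-group comparison of proportions detects with 95% certainty.

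Response is the first secondary hypothesis in Section 1.2. The sentence tells the reader that every effect the sponsor considered would be missed at most 5% of the time. If the trial then finds no significant difference in response, that sentence would support reading the result as evidence against a 25-point benefit, which the design cannot bear out in the less favourable scenarios.

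**Working it through.** **Inputs**

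- Completers: 72 in total, 36 per arm (Section 3.3). Implied loss: (90 − 72)/90 = 20%.
- Response rates: control .05 or .10; treatment .35, .40 or .45 (Section 3.3).
- Test: Fisher's exact, one binary result per Veteran (Section 5). Repeated measures and covariates therefore add nothing to this test.
- Level: not stated. Two-sided .05 is assumed, and one-sided .05 is tried as well.

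**Method**

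Exact power is the sum of Bin(x; n, p_C) × Bin(y; n, p_T) over all pairs (x, y) of control and treatment responder counts for which Fisher's p is at most .05.

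The pooled normal approximation is Φ{[Δ√n − 1.96√(2p̄q̄)] / √(p_C q_C + p_T q_T)}, with Δ = p_T − p_C, p̄ the mean of the two rates and q = 1 − p.

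**Attempt to reproduce the plan's figure at 36 per arm**

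| Control v treatment | Fisher, two-sided | Fisher, one-sided | Pooled z, two-sided | Pooled z, one-sided |
|---|---|---|---|---|
| .05 v .35 | .884 | .933 | .906 | .951 |
| .05 v .40 | .952 | .976 | .961 | .982 |
| .05 v .45 | .983 | .993 | .986 | .995 |
| .10 v .35 | .653 | .762 | .728 | .826 |
| .10 v .40 | .800 | .879 | .852 | .916 |
| .10 v .45 | .901 | .947 | .931 | .966 |

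Hand check of one cell, .10 v .35 with pooled z:

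- Δ√n = .25 × 6 = 1.5
- p̄ = .225, so √(2 × .225 × .775) = .5906
- √(.10 × .90 + .35 × .65) = √.3175 = .5635
- (1.5 − 1.96 × .5906)/.5635 = .608, and Φ(.608) = .728

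The plan's figure is not reproduced. The most generous variant tried at 36 per arm, a one-sided arcsine test, gives .841 in the worst case.

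**Ignoring dropout (45 per arm)**

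Fisher two-sided gives .947, .984, .996, .76, .889 and .957, so three of six exceed .95. Across all the test variants tried, the worst case is at most .905.

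**What would make the sentence true**

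- At 72 per arm, pooled z for .10 v .35 is [.25 × 8.485 − 1.96 × .5906]/.5635 = 1.71, and Φ(1.71) = .956. The other five cases are at least .990, so all six pass.
- With the planned Fisher test at 72 per arm, the worst case is .944, so the sentence would still narrowly fail.
- Power of .95 for .10 v .35 needs about 70 per arm with pooled z and about 75 with Fisher.

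**At the earlier trial's rates (.08 v .56)**

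Fisher power with 36 per arm is .995.

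**Side check on the HAM-D figure**

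Section 3.3 does not print its SD. Dividing the earlier trial's 7.30-point difference by the d of 1.59 in Section 2 implies 7.30/1.59 = 4.59. With that SD and no covariates, 2.5 points is the difference detectable with 90% power at 72 per arm. At 36 per arm the detectable differences are 3.07 points (80% power) and 3.56 points (90% power). This is only a reason to ask which number was used.

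**The case against.** The arithmetic was not disputed. The objections concern what surrounds it.

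- **Unstated level.** The exact range and the count of two in six rest on two-sided .05, and one of the two passing cells is only .952. This stands as a condition on the figures. It does not save the sentence, because no variant tried at 36 or 45 per arm brings all six cases above .95, and a multiplicity adjustment could only lower power.
- **Total used as per-arm number.** This explanation needs both the wrong number and a test other than the planned one, since Fisher at 72 per arm gives .944. That is fair. The explanation is a conjecture, and the error does not depend on it.
- **HAM-D.** Section 3.3 takes its SDs from control-group baseline data and adjusts for baseline HAM-D and demographics; the side check does neither. If the covariates correlate about .58 with the outcome, the 80% difference at 36 per arm falls to 3.07 × √(1 − .58²) ≈ 2.5 points. The primary figure may therefore be right, and no error is claimed there.
- **Importance.** This is a secondary outcome, the one-in-three risk belongs to the worst of six cases, and at the earlier trial's rates power is .995. All true. But the sponsor chose to plan on smaller effects and gave a power for them that the design does not have.

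**Conclusion.** The concern holds: the sentence is wrong as written. Under two-sided .05 with 36 completers per arm and Fisher's exact test, four of the six cases fall short of .95. The worst is .653, about 30 points below the claim, which leaves a 35% chance of missing a true difference of .10 against .35. The assumed level affects the exact figures but not the conclusion. The error is confined to the stated power of a secondary comparison. It does not affect the validity of the planned test, and the trial remains well powered for response if an effect near the earlier trial's recurs. The origin of the error is not established.

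**What to change.** State the significance level and sidedness for the responder test, then replace the sentence in Section 3.3. If two-sided .05 is intended, suitable wording is: *With 36 completers per arm, Fisher's exact test at two-sided .05 has power .88 to .98 if the control response rate is .05, and .65 to .90 if it is .10.* If another level is chosen, recompute on that basis.

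In the same edit, record the number per arm, the SD, the covariate correlation and the target power behind the 2.5-point HAM-D difference, and confirm that 36 per arm was used.

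The cost is wording and a short recalculation. The stated power becomes less favourable; enrolment, design and analysis are unchanged.
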